10.1.3 Additional exploratory analysis of the Primary Endpoint (COHORT 1)

Analysis of the Global Health Status at all time points (baseline, 1 month, 6 month, and 12 months) will use a normal repeated measures model with unstructured covariance matrix. Subjects with missing Global Health Status will be excluded from the analysis. Multiple imputation may be used in a sensitivity analysis. Change from baseline to each of the follow up times will be the focus of the exploratory analysis.

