10.1.2 Handling of missing items in the Global Health Status

If at least half the items in the Global Health Status are present then the Global Health Raw Score will be calculated as the average of the items that are present. This method is effectively equivalent to replacing missing items by the average of the items that are present, and is a standard method for treating summary scores with missing items. If more than half the items are missing the Global Health Status will be treated as missing. Subjects with missing Global Health Status will be excluded from the primary analysis. This method provides valid estimates provided data is missing at random (MAR). Sensitivity analyses may be performed with multiple imputation used to impute missing data.

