10.1.6 Sample Size Evaluation

We base the sample size on the precision of estimation of the Global Heath Status from QLQ-C30. The hypothesis to be tested is that the mean Global Health Status will be the same or higher one month after treatment in the Experimental Arm compared to the Control Arm. The EORTC QLQ-C30 reference values manual gives the means and SD of the Global Health Status in genitourinary cancer patients as 62.6 ± 22.2 points. We assume a standard deviation of 22.2 points for power calculations. Additional assumptions are 1:1 randomization to one of two groups, a true difference of 0 points, a Gaussian response variable, a non-inferiority margin of 15 points, alpha = 0.025 (one sided), and the use of a two sample *t*-test for the primary analysis. A non-inferiority margin of 15 points was chosen for this trial based on a combination of scientific and practical considerations. In a survey of 30 clinical trials, the definition of a clinical meaningful change in quality of life questionnaire data varies widely, with margins up to 10-15 point required for clinical significance (Cocks KT, et al 2008). With these assumptions a total evaluable sample size of 96 will provide 90% power. The planned sample size of 108 randomized equally to two arms allows for a dropout rate of approximately 10%.

10.2 COHORT 2

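### Section 10.1.3 excludes subjects rather than missing visits from a four-visit repeated-measures model; read literally, this is a completers-only fit that loses precision and is not generally valid under missing at random

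*Combined protocol and SAP*

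**What the plan says.** Section 10.1.3 describes an additional exploratory analysis of Global Health Status in Cohort 1. It covers baseline and the 1-, 6- and 12-month visits and "will use a normal repeated measures model with unstructured covariance matrix". The missing-data rule follows at once: "Subjects with missing Global Health Status will be excluded from the analysis". The section adds that "Multiple imputation may be used in a sensitivity analysis" and that "Change from baseline to each of the follow up times will be the focus of the exploratory analysis".

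Section 10.1.2 has a nearly identical sentence for the one-month primary analysis: "Subjects with missing Global Health Status will be excluded from the primary analysis". It justifies that rule by missing at random (MAR). Section 10.1.1 names the visits a subject needs for the primary analysis, namely baseline and one month. Section 10.1.3 names none, and nothing else in the document says that a woman with partial data stays in the repeated-measures model.

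**The concern.** The rule removes subjects, not visits. If it applies to any of the four scores, a woman with valid baseline, 1- and 6-month forms who misses the 12-month form contributes nothing.

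This works against the chosen model. A normal model with unstructured covariance, fitted by likelihood, can use every observed score and is valid under MAR. Restricting it to women with all four scores is in general valid only if being a completer is unrelated to the scores. The MAR argument in 10.1.2 concerns exclusion at a single time point and does not carry over to four visits, where an observed early score may predict a later missing form.

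At stake are the precision of the later comparisons and, under some dropout patterns, their accuracy. Results at 6 and 12 months bear on the expectation in section 3.1 that the shorter course lowers late as well as acute side effects.

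**Working it through.** **Inputs from the document.** 108 subjects, 54 per arm (4.3, 10.1.6). Four visits (10.1.3). SD: "We assume a standard deviation of 22.2 points for power calculations" (10.1.6). Reference mean 62.6 (10.1.6). Loss of about 5% (9.1) or about 10% (10.1.6), both stated for the one-month endpoint.

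**Assumed.** Loss at 6 and 12 months, for which no rate is given; complete baseline scores; correlation between visits; dropout mechanism.

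**1. The plan's own figure.** Section 10.1.3 gives no number, so this checks only the SD and the sample size it inherits. n per arm = 2 × (1.960 + 1.282)² × 22.2² / 15² ≈ 46.0, which rounds up to 47. Exact t-test power is 0.8999 with 47 per arm and 0.906 with 48 per arm, so the stated 96 evaluable for 90% power reproduces.

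**2. Subjects kept under the literal rule.** With loss d at each of three follow-ups, completers = 108 × (1 − d)³.
- d = 5%: 108 × 0.857 = 93
- d = 10%: 108 × 0.729 = 79
- d = 15%: 108 × 0.614 = 66
- 5%, 10%, 10%: 108 × 0.95 × 0.90 × 0.90 = 108 × 0.7695 = 83

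**3. Precision, with dropout unrelated to the scores.** Take the 5%, 10%, 10% case with dropout permanent once it occurs, a common correlation ρ = 0.5 and known covariance.

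Completers only, difference between arms in change at any visit:
SE = √[2 × 2 × 22.2² × (1 − ρ) / (54 × 0.7695)] = √(985.68 / 41.55) = 4.87.

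All observed scores, one-month change:
SE = √{2 × 22.2² × [(1 − ρ²)/(54 × 0.95) + (1 − ρ)²/54]} = √[985.68 × (0.01462 + 0.00463)] = 4.36.

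For 6 and 12 months, the information from each dropout pattern (its number of subjects times the inverse covariance of the visits it observed) is summed and inverted.

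| Change from baseline at | Completers only | All observed scores | Ratio |
|---|---|---|---|
| 1 month | 4.87 | 4.36 | 1.12 |
| 6 months | 4.87 | 4.52 | 1.08 |
| 12 months | 4.87 | 4.68 | 1.04 |

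The ratios barely move at ρ = 0.4 or 0.6. With equal loss of 5% to 15% per visit, the one-month formulas give 4.61/4.36 = 1.06 up to 5.45/4.55 = 1.20.

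**4. Bias, with dropout driven by observed scores (MAR).** This was simulated in large samples with SD 22.2, ρ = 0.4 and 0.6, an assumed true course of 62.6, 62.6, 57.6, 52.6 (12-month change −10), losses of 5%, 10%, 10%, and dropout log-odds rising by 0.5 to 2 per SD of the driver. Entries are the completers' mean minus the truth, in points.

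| Dropout follows | 12-month change | 12-month level |
|---|---|---|
| Last observed score | −0.2 to −0.9 | +1.1 to +4.5 |
| Observed decline from baseline | +0.8 to +3.5 | about 0 |

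In the first row, low scorers are removed at baseline too. The completers' baseline is raised slightly more than their 12-month mean, so the level looks better while the decline looks marginally worse. In the second row, the women who fell furthest leave and part of the decline disappears. Likelihood fits to all observed scores under both kinds of mechanism (loss parameters 5% to 15%, correlations 0.5 to 0.8) recovered the true −10 as −9.9 to −10.1.

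These are biases in one arm's mean. They pass into the arm difference only as far as dropout differs between arms.

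**The case against.** - **The sentence may mean less than it says.** It does not say missing at any time point, and it nearly repeats 10.1.2, where a missing score is a single score. It could mean only that a missing visit contributes nothing, which is how this model would normally be fitted. That reading is possible, so the completers-only conclusion is tied to the literal text. The wording needs correcting either way.
- **Multiple imputation is mentioned.** It addresses the same problem, but only as something that may be done, so it secures nothing.
- **A reader might infer that the rule hides late decline, or favours whichever arm loses its sicker patients.** The documents do not support that as a general statement. They give no dropout mechanism and no late missingness rate, and section 10.1.3 focuses on change. When dropout follows the last score, 12-month change shifts slightly the other way. Masking needs dropout that follows decline. That sicker women miss more forms is also an assumption; the study calendar lets questionnaires be taken by telemedicine when a patient is ill or cannot travel.
- **The largest precision loss falls where it matters least.** One-month scores are already used in the primary t test and the covariance-adjusted sensitivity analysis, which require only baseline and one month. This stands.
- **A reader might take this as the only use of later Global Health Status.** That is not established: section 9.2 also uses the score to calculate QALYs and does not limit that to one month.
- **The analysis is exploratory and Cohort 1 is finished.** Both are true. They limit the consequence and change the form of the remedy.

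**Conclusion.** The point holds in a limited form. Read literally, 10.1.3 describes a completers-only fit that wastes scores its own model could use and lacks general validity under MAR. Under the assumed loss rates, the precision cost is moderate at one month and small at 12 months. The possible bias in 12-month change ranges from slightly exaggerating a decline to understating it by about 1 to 3.5 points, depending on an unknown mechanism; the 12-month level could be inflated by about 1 to 4 points. All these sizes rest on assumed missingness, correlation and dropout strength. The one-month non-inferiority test, its 15-point margin and its sample size are untouched, and nothing here shows that a reported Cohort 1 result is wrong.

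**What to change.** Replace the exclusion sentence in 10.1.3 with: *All subjects with at least one Global Health Status score are included; only missing visits are omitted, and the model is fitted by restricted maximum likelihood to all observed scores.* Keep the completers-only fit as a sensitivity analysis.

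Section 4.2 says that enrollment and data analysis for Cohort 1 are complete, so a silent change of wording would rewrite the plan after the fact. State which rule was actually applied and how many subjects had a score at each visit, by arm. If the rule was completers-only, report the all-available-data fit as a labelled re-analysis next to it. The cost is one sentence, one table of counts and, if needed, one re-run of an exploratory model. No new data are required.

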10.1.4 Secondary Endpoints

Vaginal HRQOL evaluation using question 48 of the EORTC EN24: "Have you felt less feminine due to your disease or treatment". This item has a four point scale. Ordinal logistic regression will be used to analyze this question, with one month value as outcome variable, treatment arm as primary predictor, and the baseline value as covariate. A non-inferiority analysis will be performed with margin equal to 6.1 points, which represents approximately $\frac{1}{2}$ standard deviation. Additional exploratory logistic regression analyses will include the values at all time points (baseline, one month, 6 months and 12 months).

Cost effectiveness. Once parameters are computed: 1) mean differences in cost and effect between treatments, 2) variances for differences in costs and effects, and 3) covariance between effectiveness and cost difference, the incremental cost-effectiveness ratio (ICER) or incremental net benefits summarizing the monetary value of the intervention will be calculated.

$$ICER = \frac{Cost_{2\text{ Fractions}} - Cost_{\text{standard care}}}{Effect_{2\text{Fractions}} - Effect_{\text{standard care}}}$$

A CE acceptability curve will be used to quantify and graphically depict uncertainty in the analysis. To consider uncertainty in parameters, probabilistic sensitivity analysis utilizing Monte Carlo simulation (i.e., second-order simulation) will be conducted. To reflect the uncertainties in costs and in effects, a gamma distribution for costs and a normal distribution for effects will be adopted. And univariate analyses will be conducted to consider an uncertainty of one parameter at a time over a range of 95% confidence interval in cost and effectiveness measures.

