9 CRITERIA FOR EVALUATION AND ENDPOINT (COHORT 1)

9.1 Primary Objective

Evaluate the non-inferiority of patient HRQOL using the Global Health Status from the QLQ-C30 in the 2 arms one month after treatment.

All patients with a valid baseline and with a follow-up QOL questionnaire at one month post treatment will be included in the analysis. We are accounting for an approximate 5 per cent drop out rate. We anticipate a high compliance rate due to the short follow up interval for the primary endpoint. Patients without valid questionnaires will not be replaced. The baseline questionnaire is considered valid if filled out and dated by the patient before the starting date of trial treatment. Reasons for missing baseline and follow-up questionnaires will be assessed.

For the evaluation of the general quality of life the EORTC (European Organization for Research and Treatment of Cancer) Core questionnaire (QLQ-C30 version 3.0) will be used (Appendix E). The EORTC QLQ-C30 is a multidimensional, cancer-specific quality of life questionnaire developed by the EORTC Study Group on Quality of Life (QOL) for repeated assessments within clinical trials. It is developed in a cross- cultural setting and has been found valid and reliable for quality of life assessments in various cancer populations, irrespective of the specific diagnosis. Optional modules developed for specific diagnostic groups or specific treatment modalities can supplement it. The QLQ-C30 contains five functional scales (physical, cognitive, emotional, social and role functioning), a global health status/quality of life scale, three symptom scales (pain, fatigue and nausea/vomiting), and six single items assessing additional symptoms (dyspnoea, insomnia, loss of appetite, constipation, diarrhoea) and perceived financial impact. For the majority of the QLQ-C30 items a 4-point Likert-type response scale is used. Exceptions are the items for the global quality of life scale (where a 7-point scale is used). All subscale and individual item responses are linearly converted to 0 to 100 scales. A higher score for a functional and global quality of life scales represents a better level of functioning. For the symptom scales and items, a higher score reflects a higher level of symptoms and decreased quality of life.

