9.2 Secondary Objectives

Cost-effectiveness (CE) analyses will be explored using cost data (i.e., treatment related costs) for 2 fractions of VCB compared to standard of care brachytherapy (3, 4, or 5 fractions). A payer's perspective will be applied for the analysis because the costs relevant to treatments will be considered. Cost for the intervention will be measured for the cost of therapy. If costs related to the intervention occurs in different years, costs will be adjusted to the most recent year US using the medical component of the Consumer Price Index (CPI). If charged amounts relevant to the treatments are available, they will be converted to costs by using cost-to-charge ratios. We will not compare charges or costs between institutions. There will be no publication of financial data from any individual participating site.

The following data will be collected retrospectively at each patient's six month visit:

- Date of First Service
- Total Professional Fees (reported in US dollars)
- Total Technical Fees (reported in US dollars)

*Subgroup analyses using available cost effectiveness data points, beyond those listed above, may be performed for patients treated at the Huntsman Cancer Institute.

Patient reported HRQOL will be utilized for effect (i.e., effectiveness side). The HRQOL measure will be based on the EORTC QLQ-30 Global Health Status and will be used to calculate Quality Adjusted Life Years (QALYs).

An additional secondary analysis is obtained from EN 24 question 48, "Have you felt less feminine due to your disease or treatment." The analysis will compare response between the two arms at the one month time point.

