10.1.1 Primary Objective

The primary objective is to evaluate the non-inferiority of patient Health Related Quality of Life (HRQOL) in the Experimental arm compared to the Control arms one month after treatment. The primary efficacy variable is the Global Health status from the EORTC QLQ-C30. The EORTC QLQ-C30 is a multidimensional, cancer-specific quality of life questionnaire developed by the EORTC Study Group on Quality of Life (QOL) for repeated assessments within clinical trials. All patients with valid non-missing baseline and one month follow up Global Health Status will be included in the analysis. See below for handling of missing items.

The primary hypothesis is that the Global Health Status is non-inferior in the Experimental Arm compared to the Control Arm. Let μ_E and μ_C be the mean Global Health status in the Experimental and Control Arms respectively. The null hypothesis (H_0) and alternative hypothesis (H_1) are

$$H_0: \mu_E - \mu_C \leq -15 \text{ and } H_1: \mu_E - \mu_C > -15$$

A two sample t test will be used for the primary analysis. As a sensitivity analysis we will use analysis of covariance with Global Health Status at one month post therapy as Gaussian response variable, treatment group as a fixed effect and baseline Global Health Status as a continuous adjustment variable.

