**APPENDIX F. EORTC QLQ – EN24**

Patients sometimes report that they have the following symptoms or problems. Please indicate the extent to which you have experienced these symptoms or problems.

During the past week:	Not at all	A little	Quite a bit	Very much
1. Have you had swelling in one or both legs?	1	2	3	4
2. Have you felt heaviness in one or both legs?	1	2	3	4
3. Have you had pain in your lower back and / or pelvis?	1	2	3	4
4. When you felt the urge to pass urine, did you have to hurry to get to the toilet?	1	2	3	4
5. Have you passed urine frequently?	1	2	3	4
6. Have you had leaking of urine?	1	2	3	4
7. Have you had pain or a burning feeling when passing urine?	1	2	3	4
8. When you felt the urge to move your bowels, did you have to hurry to get to the toilet?	1	2	3	4
9. Have you had any leakage of stools?	1	2	3	4
10. Have you been troubled by passing wind?	1	2	3	4
11. Have you had cramps in your abdomen?	1	2	3	4
12. Have you had a bloated feeling in your abdomen?	1	2	3	4
13. Have you had tingling or numbness in your hands or feet?	1	2	3	4
14. Have you had aches or pains in your muscles or joints?	1	2	3	4
15. Have you lost hair?	1	2	3	4
16. Has food and drink tasted differently from usual?	1	2	3	4

During the past week:

	Not at all	A little	Quite a bit	Very much
--	-------------------	-----------------	--------------------	------------------

17. Have you felt physically less attractive as a result of your disease or treatment? 1 2 3 4

18. Have you felt less feminine as a result of your disease or 1 2 3 4

During the past 4 weeks:

	Not at all	A little	Quite a bit	Very much
--	-------------------	-----------------	--------------------	------------------

19. To what extent were you interested in sex? 1 2 3 4

20. To what extent were you sexually active? 1 2 3 4

Answer these questions only if you have been sexually active during the past 4 weeks:

21. Has your vagina felt dry during sexual activity? 1 2 3 4

22. Has your vagina felt short and / or tight? 1 2 3 4

23. Have you had pain during sexual intercourse or other sexual activity? 1 2 3 4

24. Was sexual activity enjoyable for you? 1 2 3 4

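### Question 48 is analysed by ordinal logistic regression, but its 6.1-point non-inferiority margin needs a mean-score estimate that section 10.1.4 does not specify

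*Combined protocol and SAP*

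**What the plan says.** Section 10.1.4 describes the item and its model: "This item has a four point scale. Ordinal logistic regression will be used to analyze this question". The one-month response is regressed on arm with adjustment for the baseline response. The section then adds: "A non-inferiority analysis will be performed with margin equal to 6.1 points". It describes this margin as roughly half a standard deviation and gives neither the standard deviation nor a source.

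The other descriptions of the endpoint add nothing on method. Section 1.2.1 says that the arms will be compared. Section 9.2 says: "The analysis will compare response between the two arms at the one month time point".

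Appendix F has no item numbered 48. The matching item is number 18, printed with codes 1 to 4: "Have you felt less feminine as a result of your disease or 1 2 3 4". The number 48 fits if EN24 items are counted on from the 30 items of the QLQ-C30 in Appendix E (30 + 18 = 48).

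A 0-100 scale appears in section 9.1, within the description of the QLQ-C30: "All subscale and individual item responses are linearly converted to 0 to 100 scales".

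The primary endpoint is specified in full. Section 10.1.1 gives signed hypotheses and states: "A two sample t test will be used for the primary analysis". Section 10.1.6 adds the margin of 15 points and a one-sided alpha of 0.025.

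**The concern.** A non-inferiority conclusion needs an estimate, a margin in the same units, and a confidence limit at a stated level. For question 48 the only named model produces an odds ratio, while the margin is in points. Nothing in the plan connects the two. The conversion is not unique either, because the odds ratio that matches a shift of 6.1 points depends on how the control arm answers, and the plan gives no such distribution.

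This is one of two Cohort 1 secondary endpoints. A reader of the results cannot tell from the plan which estimate and which limit decide non-inferiority for it. Section 4.2 reports that Cohort 1 enrolment and analysis are finished, so anything settled now is settled after the data were seen.

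**Working it through.** **Check of the method on the plan's own figure.** Section 10.1.6 says: "With these assumptions a total evaluable sample size of 96 will provide 90% power". With 48 per arm, margin 15, SD 22.2, true difference 0 and one-sided alpha 0.025, the noncentral t distribution gives 90.6% power. The primary calculation reproduces.

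**Which scale the margin can be on.**
- Printed codes 1 to 4: the largest possible difference is 4 − 1 = 3, so a margin of 6.1 could never be exceeded.
- 0-100: the item takes the values 0, 33.3, 66.7 and 100. One category is 33.3 points, and 6.1 / 33.3 = 0.18 of a category. This is the only workable reading.

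**The implied standard deviation.** If 6.1 is half an SD, the SD is 2 × 6.1 = 12.2. This figure appears nowhere in the documents. Half of the Global Health Status SD in section 10.1.6 would be 22.2 / 2 = 11.1.

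**What an SD of 12.2 would mean on this item.** For a given share p in the commonest category, the spread is smallest when everyone else is in one adjacent category: SD = 33.3 × √(p(1 − p)). Setting this to 12.2 gives p(1 − p) = 0.134 and p = 0.84. So if 12.2 is a cross-sectional SD, about 84% or more of patients must give the same answer. If it is a residual SD after baseline adjustment, the bound weakens. With an assumed baseline correlation of 0.5, the marginal SD is 12.2 / √(1 − 0.25) = 14.1 and the bound is 77%. With 0.7 it is 17.1 and about 50%.

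**Odds ratio equivalent to +6.1 points.** This is solved under proportional odds for assumed control-arm splits (not at all / a little / quite a bit / very much):

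| Assumed split, % | Odds ratio |
|---|---|
| 86 / 12 / 1.5 / 0.5 | 2.48 |
| 75 / 17 / 5 / 3 | 1.71 |
| 60 / 25 / 10 / 5 | 1.50 |
| 40 / 30 / 20 / 10 | 1.39 |
| 25 / 25 / 25 / 25 | 1.34 |

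**Power if the margin is judged on the 0-100 mean difference.** True difference 0 and one-sided alpha 0.025 are carried over from the primary endpoint as assumptions.
- SD 12.2, 48 per arm: standard error 12.2 × √(2/48) = 2.49, 95% confidence interval half-width 4.9 points, power 68%.
- SD 12.2, 54 per arm (all enrolled, section 4.3): power 73%.
- SD 12.2 as a marginal SD, with an assumed baseline correlation of 0.5: 80% with 48 per arm and 84% with 54.
- SD 20 (assumed), 48 per arm, unadjusted: 32%.

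**The case against.** The margin stands in its own sentence, and the plan does not say that it applies to the odds ratio. It could refer to a second analysis of mean scores, or to expected scores derived from the ordinal model. That is right, and it defeats the tempting reading that a points margin is incompatible with this design. What stands is that neither route is written down, and no confidence limit or alpha is attached to either.

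Three further inferences go too far:
- **The margin is meaningless because the item is coded 1 to 4.** Section 9.1 converts item responses to 0-100. It does so when describing the QLQ-C30, so applying it to the EN24 is inference, but no other scale in the documents fits 6.1.
- **The direction of harm is missing.** The item wording settles it: a higher score means feeling less feminine, which is worse.
- **The test is hopelessly underpowered.** Power well below 68% requires an SD larger than the plan implies, and the documents give no response distribution. The plan also makes no power claim for this item.

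It is also fair to say that the listed objective is only to compare the arms, which the ordinal regression does. The gap concerns the non-inferiority statement in section 10.1.4, not the comparison as a whole.

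**Conclusion.** The point holds as a mismatch between the named model and the decision threshold for one secondary endpoint. The 6.1-point margin has no stated scale, estimate, confidence limit or alpha, and its half-SD basis has no source. Read on 0-100, which is an inference from section 9.1, it is 0.18 of a response category with an implied SD of about 12.2. The 84% bound applies only if that SD is cross-sectional. The power range of about 68% to 73% assumes SD 12.2, a true difference of 0, one-sided 0.025 and no baseline adjustment; a larger true SD would lower it.

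A reader might infer that an unsupported non-inferiority claim has been made and should be withdrawn. The documents contain no Cohort 1 result for this item, so they do not show that. The primary test and sample size are not affected.

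**What to change.** In section 10.1.4 and the Cohort 1 report:
1. State which scale, estimate, confidence limit and alpha were actually used for question 48, and identify it as item 18 of Appendix F.
2. Judge the 6.1 margin on the baseline-adjusted difference in mean item score at one month (0-100, higher = worse). Non-inferiority is shown only if the upper limit of the two-sided 95% confidence interval for experimental minus control is below 6.1. If this was not the analysis run, label it post hoc. Do not choose a new margin.
3. Report the ordinal odds ratio and its confidence interval alongside, with no margin-based conclusion.
4. Give the source and type of the SD behind the half-SD basis, or mark it as unsourced.

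The cost is a few sentences and, if not already run, one regression on existing data. The drawback is that the result may be inconclusive. The report should say that failing to show non-inferiority on this item is not evidence of harm.
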